4.1 Primary Objective

CONFIDENTIAL AND PROPRIETARY

This document contains information that is confidential and proprietary to Smith & Nephew PLC and Smith & Nephew, Inc. and is intended for use only by Smith & Nephew and its manufacturer. It shall not be reproduced or copied in whole or in part, nor shall the contents be disclosed by any means without prior written permission from Smith & Nephew, nor shall anyone make any use of it that is contrary to the expressed or implied wishes of Smith & Nephew

Statistical Analysis Plan	
A Pilot Randomized Controlled Trial to Evaluate an Advanced Borderless Dressing (ALLEVYN™ LIFE Non-Bordered) in the Treatment of Chronic Ulcers	Number: CT1603ALF
	ST: 1005
	Version: 1.0, 27-Jul-2018
	Page: 9 of 27

The primary objective is to estimate the effect of treatment with ALNB on HRQoL in subjects with chronic ulcers, measured using the CWIS-PSDL (Cardiff Wound Impact Schedule - Physical Symptoms of Daily Living) scale, compared to subjects receiving SC alone, over a six-week treatment period.

4.2 Key Secondary Objective

To estimate the effects of treatment with ALNB, when compared with SC alone, on HRQoL measured by the CWIS-PSDL scale at three and twelve weeks, and CWIS well-being (WB), social life (SL); global quality of life (GQ); and satisfaction with quality of life scales (SQ); at three, six, and twelve weeks.

4.3 Secondary Objectives

Secondary objectives of this study are:

- Ulcer progression (including undermining, necrotic tissue type and amount, exudate type and amount, skin color surrounding the wound, granulation tissue, epithelialization, condition of peri-wound, ulcer dimensions and healing status) at three, six, and twelve weeks
- Healthcare resource use related to the reference ulcer (including number and cost of dressings used, consultations and time used by healthcare professionals (HCP), time in hospital, number and cost of additional treatments, procedures, and investigations) over twelve weeks

4.4 Exploratory Objective

The exploratory objective of this study is to compare differences between ALNB and SC in dressing performance (including wear time, leakage, odor control, and absorption under compression) and usability (including comfort and ease of application/removal together with associated pain) at three, six, and twelve weeks

4.5 Safety Objectives

CONFIDENTIAL AND PROPRIETARY

This document contains information that is confidential and proprietary to Smith & Nephew PLC and Smith & Nephew, Inc. and is intended for use only by Smith & Nephew and its manufacturer. It shall not be reproduced or copied in whole or in part, nor shall the contents be disclosed by any means without prior written permission from Smith & Nephew, nor shall anyone make any use of it that is contrary to the expressed or implied wishes of Smith & Nephew

Statistical Analysis Plan	
A Pilot Randomized Controlled Trial to Evaluate an Advanced Borderless Dressing (ALLEVYN™ LIFE Non-Bordered) in the Treatment of Chronic Ulcers	Number: CT1603ALF
	ST: 1005
	Version: 1.0, 27-Jul-2018
	Page: 10 of 27

Safety data will be gathered throughout the twelve weeks of the study including:

- Adverse events
- Device deficiencies

5. Study Endpoints

5.1 Primary Endpoint

The change in CWIS-PSDL scale score between baseline and six weeks in each treatment group.

5.2 Key Secondary Endpoint

Subject-reported HRQoL variables (measured using the CWIS) to be compared between groups for change over three, six, and twelve weeks for the domains of:

- CWIS-SL (Social Life)
- CWIS-WB (Well-being)
- CWIS-GQ (Global Quality of life)
- CWIS-SQ (Satisfaction with quality of life)

CWIS-PSDL will also be compared at 3 and 12 weeks for.

5.3 Secondary Endpoints

Ulcer progression variables to be compared between groups at three, six, and twelve weeks including:

- Modified Bates-Jensen Wound Assessment Tool
 - Undermining
 - Necrotic tissue type
 - Necrotic tissue amount
 - Exudate type

CONFIDENTIAL AND PROPRIETARY

This document contains information that is confidential and proprietary to Smith & Nephew PLC and Smith & Nephew, Inc. and is intended for use only by Smith & Nephew and its manufacturer. It shall not be reproduced or copied in whole or in part, nor shall the contents be disclosed by any means without prior written permission from Smith & Nephew, nor shall anyone make any use of it that is contrary to the expressed or implied wishes of Smith & Nephew

Statistical Analysis Plan	
A Pilot Randomized Controlled Trial to Evaluate an Advanced Borderless Dressing (ALLEVYN™ LIFE Non-Bordered) in the Treatment of Chronic Ulcers	Number: CT1603ALF
	ST: 1005
	Version: 1.0, 27-Jul-2018
	Page: 11 of 27

- Exudate amount
- Skin color surrounding the wound
- Granulation tissue
- Epithelialization
- Condition of peri-wound
- Ulcer dimensions
- Ulcer healed status

Healthcare resource use variables (to be compared between groups over the entire twelve week study period) including:

- Dressings used (number and type for both primary and secondary dressings), including use of compression therapy
- Healthcare consultations (number and type)
- Time spent by health care providers (HCP) in treating/caring for reference ulcer
- Time in hospital (nights spent as an inpatient due to reference ulcer)
- Interventions/procedures related to the reference ulcer (number and type), including debridement of the ulcer (curette, scissors, scalpel, forceps, other)
- Concomitant therapies/treatments (number and type) used on the reference ulcer

5.4 Exploratory Endpoints

Further exploratory data will be gathered for dressing performance and usability/acceptability and compared between groups, where appropriate. Relevant variables will include:

- Dressing wear time (days)
- Dressing leakage (HCP-assessed)
- Ease of dressing application/removal (HCP-assessed)
- Dressing use (whether dressing was cut and adherence following repositioning)
- Odor control of dressing (HCP-assessed)
- Absorption under compression (HCP-assessed for subjects with LU requiring compression).

CONFIDENTIAL AND PROPRIETARY

This document contains information that is confidential and proprietary to Smith & Nephew PLC and Smith & Nephew, Inc. and is intended for use only by Smith & Nephew and its manufacturer. It shall not be reproduced or copied in whole or in part, nor shall the contents be disclosed by any means without prior written permission from Smith & Nephew, nor shall anyone make any use of it that is contrary to the expressed or implied wishes of Smith & Nephew

Statistical Analysis Plan	
A Pilot Randomized Controlled Trial to Evaluate an Advanced Borderless Dressing (ALLEVYN™ LIFE Non-Bordered) in the Treatment of Chronic Ulcers	Number: CT1603ALF
	ST: 1005
	Version: 1.0, 27-Jul-2018
	Page: 12 of 27

- Reason for dressing change (HCP-assessed)
- Pain on dressing removal (subject-reported)
- Comfort during wear (subject-reported)

5.5 Safety Endpoints

Safety data will be gathered throughout the twelve weeks of the study, including:

- Adverse events
- Device deficiencies

6. Statistical Considerations

6.1 Determination of Sample Size

Since there is no previous data upon which to base a sample size calculation, no statistical justification for the sample size is provided. Twenty-five (25) subjects were desired for the ALNB group; a 5:3 randomization ratio was selected so that approximately forty (40) subjects would be enrolled into the study. This number of subjects is based on feasibility only.

6.2 Randomisation

Subjects will be randomly assigned in a 5:3 ratio of ALNB:SC. Subjects will be stratified by ulcer type (PU, DFU, LU).

6.3 Interim Analysis

No interim analyses are planned for this study.

7. Statistical Analysis

7.1 General

Smith & Nephew's Global Biostatistics group will conduct the statistical analysis for this study. Unless otherwise stated, all significance tests and hypothesis testing will be two-sided, performed at the 5% significance level. Resulting p-values will be quoted and 95% two-sided confidence intervals will be generated where appropriate. All p-values will be

CONFIDENTIAL AND PROPRIETARY

This document contains information that is confidential and proprietary to Smith & Nephew PLC and Smith & Nephew, Inc. and is intended for use only by Smith & Nephew and its manufacturer. It shall not be reproduced or copied in whole or in part, nor shall the contents be disclosed by any means without prior written permission from Smith & Nephew, nor shall anyone make any use of it that is contrary to the expressed or implied wishes of Smith & Nephew

Statistical Analysis Plan	 Number: CT1603ALF ST: 1005 Version: 1.0, 27-Jul-2018 Page: 13 of 27
A Pilot Randomized Controlled Trial to Evaluate an Advanced Borderless Dressing (ALLEVYN™ LIFE Non-Bordered) in the Treatment of Chronic Ulcers	

rounded to three decimal places, p-values less than 0.001 will be presented as ‘<0.001’ in all tables.

Where data summaries are specified, categorical and ordinal variables will be summarized with frequencies and percentages. Continuous variables will be summarized with the following summary statistics: number of observations, mean, median, standard deviation, minimum and maximum values. All analyses will be performed in SAS 9.4 (or later).

7.2 Analysis Populations

All subjects who provide informed consent are considered study participants. Study populations are defined as follows:

- **Safety population (SAF):** all subjects who receive study treatment. This population will be used for summaries of disposition of the subjects, protocol deviations/violations, and safety.
- **Full analysis set (FAS):** following the intention to treat principle all randomized subjects who receive study treatment and attend at least one post-baseline assessment will be included. This population will be used for the primary analysis of baseline characteristics, primary variables, secondary variables and exploratory variables.
- **Per protocol (PP) population:** includes all subjects in the FAS population who have no significant protocol deviations, meet the inclusion/exclusion criteria, and did not withdraw early (except for closure at any time). This population will be used for supportive evidence of the primary variable.

7.3 Handling of Missing or Incomplete Data

Cardiff Wound Impact Schedule (CWIS)

CONFIDENTIAL AND PROPRIETARY

This document contains information that is confidential and proprietary to Smith & Nephew PLC and Smith & Nephew, Inc. and is intended for use only by Smith & Nephew and its manufacturer. It shall not be reproduced or copied in whole or in part, nor shall the contents be disclosed by any means without prior written permission from Smith & Nephew, nor shall anyone make any use of it that is contrary to the expressed or implied wishes of Smith & Nephew

Statistical Analysis Plan	
A Pilot Randomized Controlled Trial to Evaluate an Advanced Borderless Dressing (ALLEVYN™ LIFE Non-Bordered) in the Treatment of Chronic Ulcers	Number: CT1603ALF
	ST: 1005
	Version: 1.0, 27-Jul-2018
	Page: 14 of 27

If a subject does not have any CWIS data for a post-baseline visit and has at least one post-baseline score then the Last Observation Carried Forward (LOCF) method will be used to carry forward the overall CWIS score.

If a subject is only missing part of the CWIS data at a post-baseline visit, whether that is a full domain or just part of a domain, and has at least one post-baseline score then the LOCF method will be used only for this portion of the CWIS data and the domain scores and overall CWIS score will be calculated again.

For both above instances if the missing data is at the baseline assessment or there are no post-baseline assessments to carry forward then the relevant score will be left as missing.

Modified Bates-Jensen Wound Assessment Tool

If a subject has missing data for the Modified Bates-Jensen Wound Assessment tool and has at least one post-baseline score then the missing data will be handled using the LOCF method. If the missing data is at the baseline assessment or there are no post-baseline assessments to carry forward then the relevant score will be left as missing.

Condition of peri-wound

If a subject has missing data for the condition of the peri-wound and has at least one post-baseline score then the missing data will be handled using the LOCF method. If the missing data is at the baseline assessment or there are no post-baseline assessments to carry forward then the relevant score will be left as missing.

Ulcer dimensions

If a subject has missing data for any values for length, width or depth of the wound at a particular visit, and has at least one post-baseline score, then the LOCF method will be used. The only exception to this is when missing values occur and the ulcer is healed, in which case 0cm (length/ width) or 0mm (depth) shall be imputed for all missing measurements in the statistical analysis.

Ulcer healed status

CONFIDENTIAL AND PROPRIETARY

This document contains information that is confidential and proprietary to Smith & Nephew PLC and Smith & Nephew, Inc. and is intended for use only by Smith & Nephew and its manufacturer. It shall not be reproduced or copied in whole or in part, nor shall the contents be disclosed by any means without prior written permission from Smith & Nephew, nor shall anyone make any use of it that is contrary to the expressed or implied wishes of Smith & Nephew

Statistical Analysis Plan	 Number: CT1603ALF ST: 1005 Version: 1.0, 27-Jul-2018 Page: 15 of 27
A Pilot Randomized Controlled Trial to Evaluate an Advanced Borderless Dressing (ALLEVYN™ LIFE Non-Bordered) in the Treatment of Chronic Ulcers	

If the ulcer healed status is missing at a particular assessment and the ulcer was marked as healed at the previous assessment then the ulcer should be classified as healed.

If the ulcer healed status is missing at a particular assessment and the ulcer was not marked as healed at the previous assessment then the ulcer should not be classified as healed. If the baseline ulcer healed status is missing then this should also be implemented as not healed.

In cases where the wound is recorded as healed in the investigators opinion the following imputations will be made if missing values are present: Signs of critical colonisation or infection = No. Level of Exudate = None.

Healthcare resource use

If any of the healthcare resource data is missing then no missing data implementation will be used.

Dressing Change

If any of the dressing change data from the exploratory endpoints is missing then no missing data implementation will be used.

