7.4 Derived Data

Analysis Populations

- Indicator for inclusion in the safety population.
- Indicator for inclusion in the full analysis set population.
- Indicator for inclusion in the per protocol population.

Demographics, Baseline Data and Disposition Data

- Age = (Date of baseline visit – date of birth) /365.25

Note: Round down to the nearest whole number.

CONFIDENTIAL AND PROPRIETARY

This document contains information that is confidential and proprietary to Smith & Nephew PLC and Smith & Nephew, Inc. and is intended for use only by Smith & Nephew and its manufacturer. It shall not be reproduced or copied in whole or in part, nor shall the contents be disclosed by any means without prior written permission from Smith & Nephew, nor shall anyone make any use of it that is contrary to the expressed or implied wishes of Smith & Nephew

Statistical Analysis Plan	
A Pilot Randomized Controlled Trial to Evaluate an Advanced Borderless Dressing (ALLEVYN™ LIFE Non-Bordered) in the Treatment of Chronic Ulcers	Number: CT1603ALF ST: 1005 Version: 1.0, 27-Jul-2018 Page: 16 of 27

- Body Mass Index (BMI)[kg/m²] = weight [lbs] * 703.07/ (height [inches])²

Note: the 703.07 is to correct for using pounds and inches.

- Ulcer duration = Date of baseline visit – Date of ulcer onset
- Treatment duration [days] = Date of treatment discontinuation – date of baseline assessment.
- Duration between visits = Date of Study Visit_i – date of baseline assessment, where i = 2,3,4
- A flag for if the study visit occurs outside of the time range defined in the protocol i.e. Study Visit 2 should occur on Day 21 ± 3 days, Study Visit 3 should occur on Day 42 ± 4 days, End of Study Visit should occur on Day 84 ± 4 days.

Cardiff Wound Impact Schedule

- CWIS PSDL Score =
$$\frac{\text{Sum of PSDL item scores} - 24}{96} * 100$$
- CWIS SL Score =
$$\frac{\text{Sum of SL item scores} - 14}{56} * 100$$
- CWIS WB Score =
$$\frac{\text{Sum of WB item scores} - 7}{28} * 100$$
- The CWIS-GQ score is the number circled for “How good is your quality of life”
- The CWIS-PQ score is the number circled for “How satisfied are you with your overall quality of life”
- The below formula for individual domain increases from baseline applies to all the above mentioned CWIS domains:

CWIS domain Score increase = Score at visit_i – Score at baseline visit, i = 2,3,4

CONFIDENTIAL AND PROPRIETARY

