7.9 Analysis of Primary Endpoint

The primary objective of the study is to compare Health Related Quality of Life (HRQoL) in subjects with chronic wounds. The primary efficacy variable used to measure this objective will be the change from baseline in the CWIS-PSDL scale, over a six week treatment period.

The CWIS-PSDL scale is a 24 item questionnaire split into uses a 5 category Likert scale to answer each item with a 1 - 5 score assigned to each category. The first 12 items focus on whether the subject has experienced any of the items over the past 7 days [Not at all/Not applicable – 5, Seldom – 4, Sometimes – 3, Frequently – 2, Always – 1]. The

CONFIDENTIAL AND PROPRIETARY

This document contains information that is confidential and proprietary to Smith & Nephew PLC and Smith & Nephew, Inc. and is intended for use only by Smith & Nephew and its manufacturer. It shall not be reproduced or copied in whole or in part, nor shall the contents be disclosed by any means without prior written permission from Smith & Nephew, nor shall anyone make any use of it that is contrary to the expressed or implied wishes of Smith & Nephew

Statistical Analysis Plan	 Number: CT1603ALF ST: 1005 Version: 1.0, 27-Jul-2018 Page: 20 of 27
A Pilot Randomized Controlled Trial to Evaluate an Advanced Borderless Dressing (ALLEVYN™ LIFE Non-Bordered) in the Treatment of Chronic Ulcers	

last 12 items focus on how stressful the experience of the items has been over the past 7 days [Not at all/Not applicable – 5, Slightly – 4, Moderately – 3, Quite a bit – 2, Very applicable – 1]. These scores are then transformed into a 0-100 scale at each time point, where a high score represents a 'good' HRQoL and a low score represents a 'poor' HRQoL, using the following formula:

$$PSDL\ Score = \frac{\text{Sum of item scores} - 24}{96} \times 100$$

The increase in CWIS-PSDL score between baseline and 6 weeks will be derived as follows:

$$PSDL\ score\ increase = (Score\ at\ 6\ weeks - Score\ at\ baseline)$$

Subject responses to individual items at each assessment will be summarized using counts and percentages, by treatment (and overall), wound type and amount of exudate at baseline.

The CWIS-PSDL score at Baseline and 6 weeks will be summarized as a continuous variable by treatment, wound type (and overall) and level of exudate at baseline.

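### A partly answered CWIS domain is completed from an earlier visit, or left unscored at week 3, instead of being scored from that visit's own answers

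*SAP*

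**What the plan says.** SAP 7.3 treats a partly missing post-baseline CWIS by last observation carried forward (LOCF) at the level of the missing part, "whether that is a full domain or just part of a domain", provided the subject has at least one post-baseline score: "the LOCF method will be used only for this portion of the CWIS data". Domain scores are then recalculated. Where "there are no post-baseline assessments to carry forward then the relevant score will be left as missing", nothing is imputed.

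SAP 7.4 and 7.9 define the PSDL score as a plain sum: "The CWIS-PSDL scale is a 24 item questionnaire", each item "with a 1 - 5 score assigned to each category", with 24 subtracted and the result divided by 96 and multiplied by 100. No minimum number of answered items is given, and there is no rule for scoring fewer than 24. Week-3 PSDL is a key secondary endpoint, analysed in the same way as the primary (SAP 7.10).

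If LOCF was used for PSDL at week 6, the sensitivity analysis in SAP 7.9 repeats the primary model with no imputation at all.

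Protocol 9.2.4 to 9.2.6 tell sites to check that the CWIS has been completed properly, with one valid answer to every item.

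**The concern.** A score is meant to describe the subject at one visit. Under item-level LOCF, a week-6 score can be part week 6 and part week 3. If quality of life is changing, the carried items pull the score towards the earlier state.

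The second branch of the rule loses information outright. Week 3 is the first scheduled post-baseline CWIS, so a single blank there usually has nothing to carry, and a sum over 24 items cannot be formed from 23. SAP 7.3 does not say whether the score left missing is that of the item or of the domain, but the domain is lost either way.

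The sensitivity analysis does not help, because without imputation the incomplete week-6 form drops out. In neither analysis is an incomplete form scored from its own answers. What is at stake is some precision in a trial of about 40 subjects whose stated purpose is estimation.

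**Working it through.** **Inputs from the documents.** PSDL has 24 items scored 1 to 5 and a 0-100 scale (SAP 7.9). The items are 12 problems asked twice, once for experience and once for stress (Protocol Appendix 21.2). N is about 40, with 25 on ALNB at 5:3 (SAP 6.1). Visits fall on Day 21±3 and Day 42±4 (SAP Table 3.1).

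**The plan's own figures.** A sum of 24 gives (24 − 24)/96 × 100 = 0, and a sum of 120 gives (120 − 24)/96 × 100 = 100, so the stated range is reproduced. For N, 25 + 25 × 3/5 = 40.

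**Weight of one carried item.** One category is 100/96 = 1.04 points. The largest error is 4 × 100/96 = 4.17 points.

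**Worked example.** Let every item be 3 at week 3 and 4 at week 6. The complete week-6 score is (96 − 24)/96 × 100 = 75.0. With items missing at week 6:

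| Items carried | Sum | LOCF score | Scored from answered items |
|---|---|---|---|
| 1 | 95 | 73.96 | 75.0 |
| 2 | 94 | 72.92 | 75.0 |
| 4 | 92 | 70.83 | 75.0 |

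**Simulation.** There were 20,000 subjects per setting, with assumed item variances and correlations and with items missing at random. Errors are per affected score, against the complete score.

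| Mean change per item | Items missing | LOCF bias / RMSE | Same-visit mean, bias / RMSE |
|---|---|---|---|
| 0 | 1 | 0.00 / 1.00 | −0.01 / 0.96 |
| 0.5 | 1 | −0.47 / 1.12 | 0.00 / 0.89 |
| 1.0 | 1 | −0.91 / 1.35 | 0.00 / 0.83 |
| 1.0 | 4 | −3.63 / 4.59 | 0.00 / 1.86 |

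With no mean change and one missing item, LOCF is unbiased and only slightly noisier. The simulation averaged over all answered items and had no block structure. Random missingness favours the same-visit mean.

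**Unscored forms at week 3.** Let q be the item non-response rate (an assumption). With independent skips, the share of forms with at least one blank is 1 − (1 − q)^24. If the experience and stress items for the same problem are always skipped together, it is 1 − (1 − q)^12. If p is the share lost, the confidence interval widens by a factor of about 1/√(1 − p).

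| q | Independent skips | Of 40 forms | CI width factor | Pairs skipped together |
|---|---|---|---|---|
| 0.1% | 2.4% | 0.9 | 1.01 | 1.2% |
| 0.5% | 11.3% | 4.5 | 1.06 | 5.8% |
| 1% | 21.4% | 8.6 | 1.13 | 11.4% |

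**Reach into the treatment difference.** At q = 1%, a form has on average 24 × 0.01 = 0.24 blank items. Suppose the arms differ by 0.4 category in their mean change between the two visits (assumption). The bias in the difference is then 0.24 × 0.4 × 1.04 = 0.10 point. With an assumed SD of 10 to 20, the standard error of the difference is SD × √(1/25 + 1/15) = 3.3 to 6.5 points.

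**The case against.** The strongest objection is that this will seldom matter. Sites must obtain a valid answer to every item, and every PSDL item offers a not-applicable choice, so an irrelevant question need not be left blank. The documents give no non-response rate. Bias from carried items cancels in the difference if both arms change alike, and otherwise comes to about a tenth of a point in the example above. The trial is a pilot with no confirmatory aim, and SAP 7.9 adds a repeated-measures analysis. All of this stands and limits the point to a refinement.

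Three stronger readings are tempting, and the documents do not support them.

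- A reader might infer that the SAP throws away the items answered at the visit. It does not: LOCF is confined to the missing portion, and the domain is recalculated with the answered items in it. They are only not used to estimate the blanks.
- A reader might infer that carried answers are always at least three weeks old, or that week 3 never has an earlier answer. The windows allow Day 24 and Day 38, a gap of 14 days. SAP Table 3.1 also schedules a CWIS at treatment discontinuation, which may precede week 3.
- A reader might infer that unscored week-3 forms undermine the primary endpoint generally. That needs the same subject to have an incomplete week 3 and also to lack answers at week 6. For a partly blank week 6, the answered week-3 items may still be usable, although SAP 7.3 does not say whether an incomplete earlier form meets its condition of one post-baseline score.

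What remains is that no rule in either document scores a partly answered domain from its own visit.

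**Conclusion.** The point holds as a low-cost improvement. The rule in SAP 7.3 can mix two visits in one score and normally leaves a week-3 domain unscored for a single blank. Per carried item the error is bounded at 4.17 points. The loss at week 3 is the larger of the two effects, but its size rests wholly on an assumed non-response rate and on how skips cluster.

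The 21% figure should not be read as a forecast: it is the independent-skip result at an assumed 1%, falls to about 11% if paired items are skipped together, and takes no account of the site checks. Nor is there support for claiming a material distortion of the ALNB-SC comparison.

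The advantage of same-visit scoring assumes that unanswered items resemble the answered ones. The point concerns partly answered PSDL, social life and well-being domains only. It does not touch the two single-item global scales or a wholly missing domain.

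**What to change.** In SAP 7.3, for post-baseline visits only, replace item-level LOCF with the following.

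- **Minimum.** PSDL: at least 6 of 12 items answered in each of the experience and stress blocks. Social life: at least half in each block. Well-being: at least 4 of 7.
- **If met.** Score the domain from the mean of the items answered at that visit times the number of items, taken within block for PSDL and social life.
- **If not met.** Treat the domain as wholly missing and apply the SAP's existing rule for a missing domain. A subject with a few answers is then handled like a subject with none.
- **Unchanged.** The two single-item scales and baseline. The protocol already provides for withdrawal and replacement when the Visit 1 CWIS is incomplete (Protocol 7.6).

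The block condition stops a completed experience page from standing in for a blank stress page, which asks something different.

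The cost is a few sentences in the SAP and no new data. There are two downsides. The rule assumes that unanswered items resemble the answered ones in the same block at that visit, and below the minimum the few answers given at that visit are not used. The threshold of one half is a convention, not taken from the documents, and should be stated as such.
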